## 10. ADVERSE EVENTS

### 10.1 Definitions

#### 10.1.1 Adverse Event

The term “adverse event” includes any sign, symptom, syndrome, or illness that appears or worsens in a subject during the period of observation in the clinical study and that may impair the wellbeing of the subject. The term also covers laboratory findings or results of other diagnostic procedures that are considered to be clinically significant (e.g., that requires unscheduled

diagnostic procedures or treatment measures, or result in withdrawal from the study).

The adverse event may be:

- A new illness/condition;
- Worsening of a sign or symptom of the condition under treatment, or of a concomitant illness/condition;
- An effect of the study drug; or
- A combination of 2 or more of these factors.

No causal relationship with the study drug or with the clinical study itself is implied by the use of the term “adverse event.”

Surgical procedures themselves are not adverse events; they are therapeutic measures for conditions that require surgery. The condition(s) for which the surgery is required may be an adverse event. Planned surgical measures permitted by the clinical study protocol and the condition(s) leading to these measures are not adverse events.

When a clear diagnosis is available that explains the abnormal objective findings, this diagnosis will be recorded as an adverse event and not the abnormal objective findings (*e.g.*, viral hepatitis will be recorded as the adverse event and not the transaminase elevation). If a definitive diagnosis is not available, then the sign(s) (*e.g.*, clinically significant elevation of transaminase levels) or symptom(s) (*e.g.*, abdominal pain) will be recorded as the adverse event. Adverse events fall into the categories “serious” and “non-serious.”

### **10.1.2 Serious Adverse Event**

A serious adverse event is one that at any dose of the study drug or at any time during the period of observation:

- Results in death
- Is life-threatening (defined as an event in which the subject was at risk of death at the time of the event; it does not refer to an event which hypothetically might have caused death if it were more severe)
- Requires inpatient hospitalization or causes prolongation of existing hospitalization (see note below for exceptions)
- Results in persistent or significant disability/incapacity
- Is a congenital anomaly/birth defect
- Is an important medical event, defined as a medical event that may not be immediately life-threatening or result in death or hospitalization but, based on appropriate medical and scientific judgment, may jeopardize the subject or may require intervention (*e.g.*, medical, surgical) to prevent one of the other serious outcomes listed above. Examples of such events include but are not limited to intensive treatment in an emergency department or at home for allergic bronchospasm; blood dyscrasias or convulsions that do not result in hospitalization. “Medically important” should be marked only if no other serious criteria are met.

An “unexpected SAE” is any SAE for which the nature, specificity or severity is not consistent with the currently known adverse event profile of the investigational agent(s) and not listed in the current TAS-102 Global IB.

**NOTE:** The following hospitalizations are not considered SAEs in UFHCC clinical studies:

- a visit to the emergency room or other hospital department lasting less than 24 hours that does not result in admission (unless considered an “important medical event” or a life-threatening event)
- elective surgery planned before signing consent
- admissions as per protocol for a planned medical/surgical procedure
- routine health assessment requiring admission for baseline/trending of health status (eg, routine colonoscopy)
- medical/surgical admission for purpose other than remedying ill health state that was planned before study entry. Appropriate documentation is required in these cases.
- admission encountered for another life circumstance that carries no bearing on health status and requires no medical/surgical intervention (e.g., lack of housing, economic inadequacy, caregiver respite, family circumstances, administrative).

#### **Clarification of the difference in meaning between “severe” and “serious”**

The term “severe” is often used to describe the intensity (severity) of a specific event (as in mild, moderate, or severe myocardial infarction); the event itself, however, may be of relatively minor medical significance (such as severe headache). Any grade  $\geq 3$  adverse event per CTCAE is generally considered severe AE. This is not the same as “serious,” which is based on the outcome or action criteria usually associated with events that pose a threat to life or functioning. Seriousness (not severity) serves as a guide for defining regulatory reporting obligations.

#### **10.1.3 Non-Serious Adverse Event**

A non-serious adverse event is any adverse event not meeting any of the serious adverse event criteria.

#### **10.2 Period of Observation**

Following the subject’s written consent to participate in the study, all SAEs must be collected, including those thought to be associated with protocol-specified procedures. Collection of all SAEs must continue for 30 days after the last administration of the investigational product or until the start of new anti-tumor therapy, whichever comes first. If applicable, SAEs must be collected that relate to any later protocol-specified procedure (e.g., a follow-up skin biopsy). The investigator should notify the DISC of any SAE occurring after this time period that is believed to be related to the investigational product or protocol-specified procedure.

The investigator will begin collecting non-serious adverse event (NSAE) information at screening. This NSAE information should also be collected from the start of a placebo lead-in period or other observational period intended to establish a baseline status for the subjects. Treated subjects, including those who were prematurely discontinued from the study, will be followed for any adverse events that occur during the study until 30 days following the last dose of study treatment

(i.e., the Follow-up Visit). However, if another course of anti-cancer therapy is initiated prior to the 30-day follow-up period visit, collection of adverse events will no longer be performed, with the exception of events that may be possibly, probably, or definitely related to the investigational agent or are clinically significant.

### **10.3 Documenting and Reporting of Adverse Events by Investigator**

All adverse events must be fully recorded in the subject's case record form.

Documentation must be supported by an entry in the subject's file. A laboratory test abnormality considered clinically relevant, e.g., causing the subject to withdraw from the study, requiring treatment or causing apparent clinical manifestations, or judged relevant by the investigator, should be reported as an adverse event. Each event should be described in detail along with start and stop dates, severity, relationship to investigational product, action taken and outcome.

Every attempt should be made to describe the adverse event in terms of a diagnosis that encompasses the component signs and symptoms. If only nonspecific signs or symptoms are present, then these should be recorded as separate diagnoses on the pages of the case report form.

All subjects who have adverse events, whether considered associated with the use of study drug or not, must be monitored to determine the outcome. The clinical course of the adverse event will be followed according to accepted standards of medical practice, even after the end of the period of observation, until a satisfactory explanation is found or the Principal Investigator considers it medically justifiable to terminate follow-up. Should the adverse event result in death, a full pathologist's report should be supplied, if possible.

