### 2.2 Secondary

- To evaluate the qualitative and quantitative toxicities, and reversibility of toxicities, of this treatment by NCI CTC Version 4.0.3 criteria
- To determine the progression-free survival, in months, of subjects receiving TAS-102 for the treatment of unresectable or metastatic recurrent squamous cell lung cancers
- To determine the percentage of subjects who derive clinical benefit (objective response + stable disease)
- To determine the median duration of responses in months
- To determine the overall survival in months

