### **5.3.3 Hematologic Toxicity**

Grade 1, 2 and 3 myelosuppression (neutropenia, thrombocytopenia), with recovery to pre-treatment lab criteria as specified in the inclusion criteria, does not require dose modification. Grade 3 or 4 lymphopenia does not require dose reduction. Patients with a febrile Grade 4 neutropenia >7 days or Grade 4 neutropenia associated with fever (one reading of oral temperature > 38.5° C, or three readings of oral temperature > 38.0° C in a 24-hour period) or Grade 4 thrombocytopenia >7 days should be retreated after recovery at a one-dose level reduction during subsequent cycles. If any of these toxicities recurs, the patient should be dose reduced again in all subsequent cycles after recovery to pre-treatment lab criteria as specified in the inclusion criteria. Patients will not be eligible for further treatment if resolution of toxicities requires a greater than 2-week delay in the start of the next cycle. Patients who need two dose level reductions of TAS-102 will discontinue from the study.

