### 7.4 End of Treatment

Patients should be seen in the clinic or contacted by telephone to determine if any serious or non-serious adverse events have occurred within 28 days ( $\pm$  3 days) of termination of TAS-102 dosing.

Patients will be followed for 28 days after completion of the last course of any therapy for the documentation of adverse events and concomitant medications.

Off-therapy measurements:

- a. Toxicity assessment, interim medical history and physical examination
- b. Laboratory studies:
  - CBC with differential count
  - CMP

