### **11.4 Analysis of Safety Data**

Patients will be examined and graded each cycle for subjective/objective evidence of developing toxicity according to NCI-CTC version 4.03 toxicity criteria. Incidence tables will be generated to summarize incidence of patients reporting at least one episode of each specific adverse event, incidence of adverse events causing withdrawal, and incidence of serious adverse events. Patients will have laboratory values assessed weekly during the first cycle, and in the absence of grade 3 or 4 toxicity, will subsequently have laboratory monitoring every cycle from cycle 2 onward. In the absence of significant treatment-related abnormalities, in subsequent courses patients will not require weekly laboratory evaluation, but will require the documentation of return to baseline values prior to the initiation of subsequent courses of therapy. All patients experiencing toxicities

will require the documentation of return to baseline values prior to the initiation of subsequent courses of therapy.

All patients who received study drug will be included in the safety analysis of this combination regimen. Adverse event data and corresponding toxicity grades during treatment and during long-term follow-up will be summarized in the form of tables. Incidence tables will be generated to summarize incidence of patients reporting at least one episode of each specific adverse event, incidence of adverse events causing withdrawal and incidence of serious adverse events. The total number of episodes for each event reported (Frequency Table), the severity and attribution to study therapy of each episode reported (Severity Table and Attribution Table) will also be displayed. Listings of adverse events by patients will include the time to onset, the duration of each event, the severity of each event, and the relationship of the event to study therapy, whether it was a serious event, and whether it caused withdrawal. Safety data will be summarized for the overall patient group and by dose levels. Dose-toxicity curves will be fitted to the final data to estimate the toxicity rates of each dose levels.

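### Laboratory toxicity rates rest on investigator judgement rather than on the scheduled blood counts and can be too low; separately, sections 7.4 and 10.2 end adverse-event collection at different times

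*Combined protocol and SAP*

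**What the plan says.** **Objective.** The first secondary objective in section 2.2 reads "To evaluate the qualitative and quantitative toxicities, and reversibility of toxicities, of this treatment by NCI CTC Version 4.0.3 criteria". Section 11.2 plans exact 95% binomial intervals for toxicities and their reversibility.

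**When a laboratory value becomes an adverse event.** Section 10.1.1 states: "The term also covers laboratory findings or results of other diagnostic procedures that are considered to be clinically significant". Section 10.3 adds "A laboratory test abnormality considered clinically relevant, e.g., causing the subject to withdraw from the study, requiring treatment or causing apparent clinical manifestations", and the sentence goes on "or judged relevant by the investigator, should be reported as an adverse event". Neither section names a CTCAE grade as a trigger. Section 10.3.2 ties CTCAE grading to physical signs or symptoms and does not mention laboratory values.

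**What is tabulated.** The incidence tables in section 11.4 "summarize incidence of patients reporting at least one episode of each specific adverse event". The frequency, severity and attribution tables and the patient listings also start from reported events. The section mentions toxicity grading each cycle and laboratory monitoring, but plans no table of laboratory values by grade.

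**What is measured.** Section 7.1 schedules a CBC at baseline and on Days 1 and 15 of every cycle, and a metabolic panel at baseline and on Day 1. Both are weekly in Cycle 1.

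**When collection ends.** Section 7.4: "Patients will be followed for 28 days after completion of the last course of any therapy for the documentation of adverse events". It also sets a contact about events within 28 days (± 3) of the end of dosing. Section 10.2: treated subjects "will be followed for any adverse events that occur during the study until 30 days following the last dose of study treatment".

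**The concern.** Section 9.1.7 presents severe myelosuppression as a leading warning for this drug, with Grade 3-4 neutropenia at 38%. This toxicity is defined by a blood count, and the trial takes the counts on a schedule. Yet the reported rate comes from whichever counts an investigator chose to enter as adverse events. Two sites with identical counts could report different rates. A cytopenia that is never entered also drops out of the reversibility estimate, although recovered events are what that estimate is about.

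The second matter is smaller. Two sections give different ends to adverse-event collection, so a site can follow one and fall short of the other.

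**Working it through.** No figure in the plan underlies this point, so there is none to reproduce. The check sets the sections side by side and adds a small illustration.

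**1. Can a graded cytopenia go unrecorded?**
- Dosing in a cycle ends on Day 12 (section 5.1), so a low count on Day 15 has no remaining dose in that cycle to interrupt.
- Section 5.3.3 says that "Grade 1, 2 and 3 myelosuppression (neutropenia, thrombocytopenia), with recovery to pre-treatment lab criteria" does not call for dose modification.
- If the count has recovered by the next Day 1 and the patient had no symptoms and no treatment, none of the examples in section 10.3 applies. Only the investigator's judgement remains.
- If the event is not entered, no table in section 11.4 shows it.

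**2. How much could this matter?** Inputs: Grade 3-4 neutropenia 38% (section 9.1.7); N = 30, the maximum enrolment (section 3.1). The share *s* of these events that is recorded is **not in the documents** and is assumed here.

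Expected true count: 0.38 × 30 = 11.4. Recorded count: x = 11.4 × s, rounded. Exact (Clopper-Pearson) limits: the 0.025 quantile of Beta(x, 30 − x + 1) and the 0.975 quantile of Beta(x + 1, 30 − x).

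| Assumed share recorded | x | Rate | Exact 95% CI |
|---|---|---|---|
| 100% | 11 | 36.7% | 19.9% to 56.1% |
| 75% | 9 | 30.0% | 14.7% to 49.4% |
| 50% | 6 | 20.0% | 7.7% to 38.6% |

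The interval reflects sampling error only and gives no sign that events are missing. At half recorded, its upper limit only just reaches the assumed true rate of 38%.

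**3. Collection window.**
- If both periods run from the last dose, they differ by 30 − 28 = 2 days.
- If the ± 3 days is read as the timing of the contact, it falls between Day 25 and Day 31. A Day 25 contact leaves Days 26 to 30 uncovered, 30 − 25 = 5 days. A Day 28 contact leaves 2 days, and a Day 30 or 31 contact leaves none.
- The anchors also differ: completion of the last course in section 7.4, last dose in section 10.2. If a course means the 28-day cycle and the last dose is on Day 12, section 7.4 runs to (28 − 12) + 28 = 44 days after the last dose, longer than section 10.2. Depending on the reading, section 7.4 is therefore either shorter or longer than section 10.2.

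**The case against.** The strongest reply is that nothing forbids recording an asymptomatic cytopenia. The triggers in section 10.3 are examples, and the judgement clause is open-ended. Section 11.4 has patients graded each cycle by CTC criteria, and section 7.1 schedules a toxicity assessment on Day 1 of each cycle. Counts that alter dosing are hard to call irrelevant, since section 10.3.3 records the action taken with the drug. This stands against any claim that the rates *will* be too low. It does not supply an objective trigger, and no laboratory table is tied to the grading.

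Four stronger readings are tempting but unsupported:
- *The recorded rate could fall to about 4%, the febrile neutropenia rate.* That assumes almost every other event goes unrecorded. The documents give no recording share.
- *Section 5.3.3 tells sites to ignore recovered Grade 1-3 myelosuppression.* It is a dose rule and does not govern recording.
- *Neutropenia will be split across two terms.* Section 9.1.9 does show Grade ≥3 Neutropenia at 107/646 = 16.6% and Neutrophil Count Decreased at 142/646 = 22.0%. But that is a MedDRA table from the Investigator's Brochure, section 11.4 specifies no such coding for this trial, and a split loses no event. The two lines sum to 38.5%, close to the 38% in section 9.1.7, so that dataset does not point to heavy under-recording. Its recording rule is not given, however, and a patient may appear on both lines.
- *Deaths could be missed in the window gap.* Section 6.2 requires deaths within 30 days of stopping to be notified and survival status to be followed, and section 7.5 continues follow-up until death. Section 10.2 also asks for later related SAEs to be notified.

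On the window, the ± 3 days in section 7.4 may describe the interval in which events occurred rather than the contact date. That ambiguity is itself a reason to reword it.

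**Conclusion.** The point holds at moderate size. Laboratory toxicity rates, as planned, depend on investigator judgement when the scheduled counts could supply them directly, and they can be too low. By how much is unknown. The fall from 11/30 to 6/30 rests on an assumed true rate of 38% and an assumed 50% recording share, and is an illustration only.

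The 28-day and 30-day rules conflict in length and anchor. The exposure is at most 5 days, assuming that both periods run from the last dose and that the contact can fall on Day 25. It mainly concerns non-serious events.

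Toxicity is a secondary endpoint. The primary response analysis and the first-stage rule are not affected.

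**What to change.** **Section 11.4.** Add a table of the worst CTCAE v4.03 grade per patient for neutropenia, thrombocytopenia, anaemia and the chemistry toxicities. Derive it from all CBC and CMP values collected on treatment and up to the end of observation, regardless of judged relevance, with one line per analyte. Use this table for the laboratory toxicity rates and their exact 95% intervals, and keep the reported-event tables beside it. Show the baseline grade as well, since section 3.2 allows patients with benign ethnic neutropenia to enrol.

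**Sections 7.4 and 10.2.** Reconcile them to one end date and one anchor for adverse-event collection, and place the final adverse-event contact no earlier than that date.

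**Cost.** A little more programming on values the schedule already provides for, and a short wording change. The haematologic rates may look less favourable. The derived grade is still the worst *observed* grade, because a low point between scheduled counts stays unseen. Sample size, error rates and treatment rules do not change.

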#### **10.3.1 Assessment of Causal Relationship of Study Drug**

The Investigator will provide an assessment of the potential causal relationship between adverse events and study medication by determining whether or not there is a reasonable possibility that the event was caused by the study medication. The relationship or association of the adverse event to the study medication will be characterized as not related, probably not related, possibly related, probably related, or related:

**Not Related:** There is not a temporal relationship to the study drug administration or the adverse event is clearly due only to the progression of the underlying disease state, intercurrent illness, concomitant medication, concurrent therapy or other known cause.

**Probably Not Related:** There is little or no chance that the study drug administration caused the adverse event; the event is most likely due to another competing cause, including intercurrent illness, progression or expression of the disease state, or a reaction to a concomitant medication or concurrent therapy appearing to explain the reported adverse event.

**Possibly Related:** The association of the adverse event with the study drug administration is unknown; however, the adverse event is not reasonably attributed to any other condition.

**Probably Related:** When a reasonable temporal relationship exists between the adverse event and the study drug administration; significant symptoms abate upon discontinuation of the study drug and there is a reasonable explanation based on known characteristics of the study drug and there is no clear association with preexisting disease or therapy, intercurrent illness, concurrent therapy or other factor(s).

**Related:** When the adverse event is a known side effect of the study drug or there is a temporal relationship to the administration of the study drug; or the adverse event reappears upon re-administration of the study drug (rechallenge); or the significant symptoms of the adverse event abate upon discontinuation of the study drug (dechallenge).

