### 5.3 Dose Modifications

The National Cancer Institute (NCI) Common Toxicity Criteria for Adverse Events Version 4 (CTCAE) will be used to grade toxicity (<http://evs.nci.nih.gov/ftp1/CTCAE/About.html>).

The starting dose of TAS-102 is 35 mg/m^2 up to a maximum of 80 mg per dose (based on the trifluridine component) orally twice daily within one hour of completion of morning and evening meals on Days 1 through 5 and Days 8 through 12 of each 28-day cycle until disease progression or unacceptable toxicity. Doses will be rounded to the nearest 5 mg increment. Study medication will be administered on a 4 week schedule. Doses will be delayed or reduced for clinically significant (Grade 3-4) hematologic and non-hematologic toxicities that are related to protocol therapy according to the guidelines shown in the Dose Delays/Dose Modifications table that follows. Dose modifications will follow predefined dose levels. Dose adjustments for hematologic toxicity are based on the blood counts obtained in preparation for the day of treatment.

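### Section 10.3.1 makes *Related* easier to meet than *Probably Related*, so the causality scale is out of order and the Attribution Table in 11.4 cannot be read reliably

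*Combined protocol and SAP*

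**What the plan says.** Section 10.3.1 first asks the investigator to judge whether drug causation is reasonably possible, then gives five levels: *Not Related*, *Probably Not Related*, *Possibly Related*, *Probably Related* and *Related*.

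- *Related* applies when the event is "a known side effect of the study drug or there is a temporal relationship to the administration of the study drug". Two more routes follow, each again introduced by *or*: return of the event on re-administration, and abatement on stopping. None of the four routes mentions other causes.
- *Probably Related* applies "When a reasonable temporal relationship exists between the adverse event and the study drug administration". It also needs the symptoms to subside once the drug is stopped, a pharmacological rationale for the event, and a check on other causes, worded as "there is no clear association with preexisting disease or therapy, intercurrent illness, concurrent therapy or other factor(s". These elements are cumulative.
- *Not Related* covers events without a temporal relationship, and also events clearly due only to disease progression, intercurrent illness, other treatment or another known cause. *Probably Not Related* covers events most likely due to a competing cause. Neither is limited to events whose timing does not fit.

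The section does not say which level applies when an event meets more than one definition. Section 10.3.3, by contrast, gives a worst-case hierarchy for the action taken with study drug.

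Section 11.4 commits to displaying "the severity and attribution to study therapy of each episode reported" in a Severity Table and an Attribution Table, and to listing the relationship to therapy by patient. Section 10.2 refers to events possibly, probably or definitely related; *definitely related* is not a level of the scale.

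**The concern.** A causality scale is ordinal: each step up should need more evidence. Here the top step needs less than the one below it. *Related* is also the only one of the three upper levels that does not ask about other causes, since *Possibly Related* too requires that no other condition reasonably explains the event.

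This matters because the trial has a single open-label arm. No concurrent control group shows how much morbidity comes from the cancer, so investigator attribution is the main within-trial means of separating drug effect from disease. Toxicity is the first secondary objective in section 2.2.

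The brochure table in 9.1.9 shows the kind of event at issue. Any-grade cough was reported in 63/646 (9.8%) on TAS-102 and 33/322 (10.2%) on placebo; dyspnoea in 63/646 (9.8%) and 34/322 (10.6%). Neither shows an excess on drug, both are plausible lung-cancer symptoms, and both could be entered as *Related* on timing alone. These were not patients in this trial, so the figures only illustrate the problem.

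**Working it through.** The documents state no figure on this point, so there is nothing to reproduce. The check is on the logic of the definitions.

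**Inputs (all from 10.3.1).** Five yes/no features of an event:

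- T: temporal relationship
- K: known effect of the drug, or explanation from its known characteristics
- R: positive rechallenge
- D: positive dechallenge
- A: another cause

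**Definitions as written.**

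- *Related* = T or K or R or D
- *Probably Related* = T and D and K and not A

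**Direct argument.** Every *Probably Related* event has a reasonable temporal relationship, so it meets the timing route of *Related*. The converse fails: an event with timing only (T yes; K, R, D and A no) is *Related* but not *Probably Related*. *Probably Related* is therefore a strict subset of *Related*. This does not depend on treating known side effect and reasonable explanation as one feature K, because timing alone carries it.

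**Enumeration.**

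| | Patterns | *Related* | *Probably Related* |
|---|---|---|---|
| All patterns (2^5) | 32 | 30 | 2 |
| Timing fits (2^4) | 16 | 16 | 2 |

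*Related* fails only when T, K, R and D are all absent (2 patterns, A yes or no), so 32 − 2 = 30. *Probably Related* fixes T, D, K and A and leaves R free, giving 2. If an assessor always took the highest level met, *Probably Related* would never be used.

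**Overlap at the other end.** Of the 16 patterns with fitting timing, 8 have another cause (A yes). All 8 meet *Related*. If that cause is clearly the only one, they also meet *Not Related*; if it is the most likely one, they fit *Probably Not Related*. Two assessors could follow the text and place the same event at opposite ends of the scale.

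**Which rewording restores the order?**

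- *Timing plus at least one of K, R or D*: of the 16 timing patterns only the 2 with none of K, R, D drop out, leaving 14. Adding a no-other-cause condition leaves 8 patterns to consider; 7 pass, against 2 for *Probably Related*, both among the 7. An event with timing and a known effect but no dechallenge would be *Related* and still fail *Probably Related*. The timing-alone route has gone, but the inversion remains.
- *All of T, K, D and R, with no other cause*: 1 pattern passes, and it lies inside the 2 for *Probably Related*. The order is restored.

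These are counts of logical patterns, not expected frequencies of events.

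**The case against.** The strongest reply is that investigators do not apply such definitions mechanically. The opening sentence of 10.3.1 asks for a judgement of reasonable possibility, and two levels are written for events caused by the disease or another illness. *Not Related* also has a limb for events without a temporal relationship, which would be empty after dosing if every later event counted as temporally related; timing is evidently meant as a judgement.

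This stands, and it limits what can be claimed. A reader might infer that nearly every on-treatment event will fall in the top level. The text supports only that such events can qualify for it. The reply does not remove the defect: judgement is needed precisely because the definitions overlap, and nothing says how to resolve the overlap.

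Three further inferences are tempting and unsupported.

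- *A size taken from the placebo column.* Section 9.1.9 shows 299/322 (92.9%) placebo patients with any event and 146/322 (45.3%) with a Grade 3 or higher event. These are all-cause incidences with no attribution data. Reading them as the share that would be called *Related* assumes that no investigator would use the two levels meant for other causes.
- *An effect on dosing.* Section 5.3 ties dose changes to hematologic and "non-hematologic toxicities that are related to protocol therapy", but it does not cite 10.3.1 or say which levels count. If *Possibly Related* and *Probably Related* also count, movement among the upper levels changes nothing. The hematologic triggers listed in 5.3.1 are blood counts and febrile neutropenia.
- *An effect on the six-patient stop.* Section 6.4 speaks of intolerability requiring dose reduction and makes no use of the attribution scale.

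The reach is also limited. The Attribution Table is one display among several in 11.4; the incidence, frequency and severity displays do not need attribution. Within the observation period, serious events are collected and reported whatever their cause (10.2, 10.4.1).

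**Conclusion.** The definitions in 10.3.1 are wrong as written. *Related* is met by any one of four conditions with no exclusion of other causes, *Probably Related* needs four elements together, and the second is a strict subset of the first (2 against 16 of the 16 patterns with fitting timing). Events with fitting timing and another clear cause can meet both *Related* and *Not Related*, with no precedence rule. The Attribution Table in 11.4 therefore cannot reliably separate drug effects from lung-cancer morbidity, in a trial with no control arm to do so.

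The conclusion rests on the literal wording and needs no assumption about event rates. How many events would be misclassified depends on how investigators resolve the overlap, and the documents give no basis for a figure. The primary response endpoint, the sample size and the all-cause safety tables are unaffected. This is a real but inexpensive correction to the safety reporting.

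**What to change.** 1. Redefine *Related* so that it requires every element of *Probably Related* plus further evidence, such as positive rechallenge. Alternatively, rewrite the two definitions together so that the top level is strictly the more demanding. Asking only for timing, no likelier cause and one supporting feature is not enough unless *Probably Related* is changed as well.
2. Add a precedence rule: an event clearly due to another cause is *Not Related*, and one most likely due to another cause is *Probably Not Related*, even when the timing fits.
3. Use one set of names: replace *definitely related* in 10.2 with the matching level of the scale, or rename that level.

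The cost is a revised paragraph in 10.3.1, one term in 10.2 and the matching case report form guidance. If events have already been attributed under the current wording, they should be re-attributed under the new one before the Attribution Table is produced, or the table should state which definition each event was graded under. No sample-size or endpoint change follows.
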